6.4 Study Endpoints

6.4.1 Primary Efficacy Endpoint

- Rate of safe insertion and patency of CVCs created across venous occlusions.

6.4.2 Primary Safety Endpoints

- Acute device safety, defined as the absence of procedural complications (hemopericardium, hemothorax, pneumothorax, blood transfusion, resuscitation, emergency post-procedural intervention, transfer to an intensive care unit, and death) at discharge and 7 days post procedure.
- Overall device and procedure related anticipated adverse events compared to historical safety data from CV placement procedures.

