1.0 PROTOCOL SUMMARY

1.1 Protocol Synopsis

Study Title	Surfacer® System to Facilitate Access in Venous Occlusions
Protocol Number	BVT.Surfacer.17-01
Type and Phase	Pre-Market Investigational Device Exemption (IDE) Study
Number of Sites	Three sites will participate in the study initially, with up to 10 sites overall.
Device Name	Surfacer® Inside-Out® Access Catheter System
Indication for Use	The Surfacer® Inside-Out® Access Catheter System is intended to obtain central venous access to facilitate catheter insertion into the central venous system for patients with upper body venous occlusions or other conditions that preclude central venous access by conventional methods.
Device Description	The Surfacer® Inside-Out® Access Catheter System (Surfacer® System) is designed to facilitate entry and placement of central venous access catheters within the peripheral vasculature. The Surfacer® System is comprised of four components: a Workstation (Workstation Sheath) for percutaneous access to the femoral vein; a Delivery Instrument (Surfacer Device) which contains a Needle Wire and Needle Guide which is advanced to the supraclavicular space; an Exit Target which provides fluoroscopic guidance to mark the exit point; and an Exit (Peelable) Introducer which is introduced over the Needle Wire to access the central venous system. The Surfacer® System facilitates the entry and positioning of standard access catheters by establishing a transient passage across venous occlusions. Once the access is obtained and a catheter is in place, the Surfacer® System is removed.

Study Design	This is a prospective, single-arm, multi-center, study to demonstrate the safety and efficacy of the Surfacer® System.
Study Objectives	
This goal of this study is to demonstrate that the Surfacer® System, once in place, facilitates stable upper body central venous access that is suitable for any conventional catheter.
 
Safety will be evaluated based on the overall rate of acute complications using the study device as compared to historical rates of device/procedure related safety events using conventional CVA methods.
 
Efficacy will be evaluated by the rate of transient successful central venous accesses created by the study device.

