5.5 Surfacer System Potential Risks

Potential risks associated with using the Surfacer System are considered to be similar those associated with routine interventional procedures and with the patient's underlying condition. List of Potential Risks and Definitions can be found in Appendix A.

These potential risks include, but are not limited to:

- Pain
- Infection
- Bleeding
- Adverse tissue reaction; allergic reaction
- Cardiovascular sequelae including: perforation, tamponade, spasm or effusion
- Lymphatic system sequelae
- Pulmonary sequelae including: pneumothorax, pulmonary embolism
- Vascular sequelae including vasospasm, vessel perforation, dissection, or aneurysm
- Unintended embolization or thrombosis
- Arrhythmias
- Neurologic sequelae including stroke; transient ischemic attack; nerve injury
- Arteriovenous Fistula
- Death
- Surfacer System component failure or malfunction

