Vasospasm - A transient constriction of the lumen of one or more vessels due to contraction of vascular smooth muscle. **Vessel Perforation** - Complete penetration of the vessel wall, with or without self-limited extravasation of blood into surrounding tissues. **Vessel Dissection**- This term applies to unintended injury of femoral or pelvic vessels or the inferior vena cava. Dissection is defined as disruption of the intimal layer that can be detected by contrast angiography, ultrasound, or other imaging modalities. **Aneurysm**- an abnormal blood-filled bulge of a blood vessel and especially an artery resulting from weakening (as from disease) of the vessel.
- **Unintended Embolization or Thrombosis - Embolism** is defined as the unintended entry of air, thrombus, or foreign bodies into the circulation. **Thrombosis** - local coagulation or clotting of the blood in a part of the circulatory system.
- **Arrhythmias**- Development of a new atrial and/or ventricular arrhythmia, exacerbation of a prior arrhythmia or a significant increase in the severity of the current arrhythmia. Event that requires cardioversion or introduction of a pacemaker will be considered a Serious Adverse Event.
- **Neurologic Sequelae including stroke; transient ischemic attack; nerve injury:** **Stroke** - Acute cerebral infarction or hemorrhage confirmed by brain imaging (CT or MRI), or with new neurological abnormalities persisting more than 72 hours. A stroke that occurs within 24 hours of the procedure will be considered procedure related. All stroke events are considered serious. **Transient Ischemic Attack (TIA)** - New focal neurological deficit with rapid symptom resolution (usually 1-2h), always within 24 h. **Nerve Injury**- includes total or partial transection of a nerve from stretching, cutting (laceration), compression, shearing, or crushing injuries

- **Arteriovenous fistula** - A dilation of an artery with actual disruption of one or more layers of its walls, rather than with expansion of all wall layers. An arteriovenous fistula is an abnormal channel or passage between an artery and a vein.
- **Death** - Cessation of brain and heart activity documented by physician, laboratory or diagnostic test. Device related death is defined as death related to the investigational device. This may be a device malfunction, misuse, or any death in which the relation of the device cannot be ruled out.

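### The acute-safety primary endpoint has no catch-all: a stroke within 24 hours, or a serious unanticipated device effect, is scored as complication-free unless one of eight listed items also occurs

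*Combined protocol and SAP*

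**What the plan says.** Section 6.4.2 gives the first primary safety endpoint as "Acute device safety, defined as the absence of procedural complications (hemopericardium, hemothorax, pneumothorax, blood transfusion, resuscitation", and completes the list with "emergency post-procedural intervention, transfer to an intensive care unit, and death) at discharge and 7 days post procedure". The synopsis (1.1) and the Primary Endpoints part of 8.2.1 use the same eight items. In none of the three places is there an open-ended term or a general clause for serious related events.

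Section 5.5 names harms beyond those eight, among them "Neurologic sequelae including stroke; transient ischemic attack; nerve injury", "Unintended embolization or thrombosis" and, in one line, "Pulmonary sequelae including: pneumothorax, pulmonary embolism". Of that last pair only pneumothorax is in the endpoint. Appendix A then sets rules for some of them. For stroke: "A stroke that occurs within 24 hours of the procedure will be considered procedure related. All stroke events are considered serious". For arrhythmia: "Event that requires cardioversion or introduction of a pacemaker will be considered a Serious Adverse Event".

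The second primary safety endpoint compares overall device- and procedure-related anticipated adverse events with historical data. Section 9.1.2 takes the anticipated events from the Instructions for Use and Section 5.5. Section 9.1.3 defines an unanticipated adverse device effect as a serious, device-associated event not previously identified in the protocol in nature, severity or incidence.

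**The concern.** An endpoint presented as acute device safety should fail a subject who has a serious harm that the protocol itself attributes to the procedure. This one fails the subject only if the harm is one of eight items or leads to one.

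Stroke is the clear case. If it occurs within 24 hours, Appendix A settles both its seriousness and its relation to the procedure. A subject who has one, survives, and has no transfusion, resuscitation, emergency intervention or intensive-care transfer is still a success.

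The second case is a serious device effect of a kind nobody anticipated. It is not on the list, and the other primary safety endpoint counts only anticipated events. A pre-market device study has particular reason to capture such an event.

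At stake is the meaning of the acute-safety rate: it could be reported as 100% in a study that had such an event.

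**Working it through.** **Step 1. How each event is scored under the text as written.**

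| Event, with no listed item occurring | Serious by rule? | Procedure related by rule? | Fails acute safety (6.4.2)? | Counted in second primary safety endpoint? | In 8.3.8 tables? |
|---|---|---|---|---|---|
| Stroke within 24 hours | Yes (Appendix A) | Yes (Appendix A) | No | Yes, if anticipated per 5.5 | Yes |
| Serious unanticipated device effect | Yes (9.1.3) | Device-associated (9.1.3) | No | No, because not anticipated | Yes |
| Arrhythmia needing cardioversion or a pacemaker | Yes (Appendix A) | No rule | Unclear: the treatment may itself be a listed item | Yes, if judged related | Yes |
| Embolism, dissection, nerve injury, arteriovenous fistula | No rule | No rule | No | Yes, if judged related | Yes |

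The SAE criteria in 9.1.3 include prolonged hospitalization and persistent disability. Neither is among the eight items, so an event can be serious without triggering one. Appendix A also makes tamponade serious and procedure related, but it is defined as needing drainage and is plausibly caught as hemopericardium or emergency intervention. The two firm gaps are the first two rows.

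**Step 2. Reproduce the plan's own figures.** Section 8.2.2 uses Clopper-Pearson limits with n = 30. For x successes, the lower limit is the 0.025 quantile of Beta(x, 31 − x) and the upper limit is the 0.975 quantile of Beta(x + 1, 30 − x).

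- 15/30: 31.3% to 68.7%, as stated.
- 27/30: 73.5% to 97.9%, as stated.

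**Step 3. The same method applied to the gap.** Suppose no listed item occurs in 30 subjects.

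- No unlisted event, or such events not counted: 30/30 = 100%. The lower limit is 0.025^(1/30) = 0.884, so the interval is 88.4% to 100%.
- One such subject counted as a failure: 29/30 = 96.7%, interval 82.8% to 99.9%.
- Two such subjects counted: 28/30 = 93.3%, interval 77.9% to 99.2%.

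**Step 4. How likely is at least one?** The documents give no rate, so this is a range over assumed values. Here p is the per-subject probability of a serious related event that triggers no listed item, and the chance of at least one in 30 is 1 − (1 − p)^30.

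| Assumed p | Chance of at least one in 30 |
|---|---|
| 1% | 26% |
| 2% | 45% |
| 3% | 60% |
| 5% | 79% |

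Table 4 reports 2 complications in 136, both hematomas, and therefore none of this kind. With 0/136, the one-sided 95% upper limit is 1 − 0.05^(1/136) = 2.2% and the two-sided one is 1 − 0.025^(1/136) = 2.7%. That series mixes devices, and for one of its three sources the table gives complications as not reported. It is only a loose guide, but it points to the lower rows.

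**The case against.** The strongest reply is that little is lost. The second primary safety endpoint takes in stroke, embolism and arrhythmia through 9.1.2 and 5.5. Section 8.3.8 classifies adverse events by seriousness, by relation to device or procedure, and by whether they were anticipated, and gives rates with 95% intervals. The IDMC reviews safety, and 9.1.5 requires expedited reporting of unanticipated effects. There is no performance goal, so moving from 30/30 to 29/30 changes no decision. All of this stands, and it limits the point to how the primary endpoints score a subject.

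It can also be said that the protocol never calls the list exhaustive, and that emergency post-procedural intervention is undefined and might catch some events. Both are true. But a definition followed by a parenthesis without any open-ended term would normally be programmed as closed, whereas 5.5 expressly says that its own list is not limiting. If the list was meant to be open, its membership is undefined and the same edit is needed.

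Three stronger readings are tempting, and the documents do not support them.

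- A reader might infer that all the unlisted harms are serious and procedure related by rule. Among them, only stroke within 24 hours meets both rules. Arrhythmia needing cardioversion or a pacemaker has a seriousness rule only, and embolism, dissection, nerve injury and fistula have neither.
- A reader might infer that the stated objective goes unanswered, because 1.1 says "Safety will be evaluated based on the overall rate of acute complications using the study device". That sentence goes on to a comparison with historical rates for conventional access, which is what the second primary safety endpoint addresses.
- A reader might infer that the endpoint errs only in the device's favour. The eight-item rate can never be lower than the rate with a catch-all added. But transfusion, intensive-care transfer and death carry no stated relatedness condition, so unrelated events can also count against the device. The net direction is not established.

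**Conclusion.** The point holds in a limited form. As written, the acute-safety rate counts as a success any subject whose stroke within 24 hours, or whose serious unanticipated device effect, brings no listed item with it. For stroke and other anticipated events the defect is confined to that rate. For a serious unanticipated device effect it extends to both primary safety endpoints, leaving the 8.3.8 tables and expedited reporting as the places where it appears.

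One such subject in 30 is worth 3.3 percentage points (100% − 96.7%) and lowers the lower confidence limit from 88.4% to 82.8%. This rests on reading the list as closed, on 30 evaluable subjects, and on no listed item occurring in anyone. How often it would happen is unknown. The study is descriptive, so the consequence is a misleading summary figure and not a wrong test result.

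**What to change.** In 1.1, 6.4.2 and the Primary Endpoints part of 8.2.1, add to the list: 'or any other serious adverse event related to the device or the procedure'. Report each component separately, and report the present eight-item version alongside so that nothing now planned is lost.

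No new visits, assessments or subjects are needed. The schedule in 1.3 already collects procedural complications and adverse events during the procedure, at discharge and at day 7, and 8.3.8 already classifies events by seriousness and by relation to device or procedure. Because 9.1.1 grades relation to the device only, confirm that the case report form also records relation to the procedure, which 8.3.8 needs in any case.

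The cost is one phrase in three places and a few table lines. The acute-safety rate may be slightly less favourable.

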4.3 Proof of Concept Study (Elayi 2011)

Elayi CS, Allen CL, Leung S, Lusher S, Morales GX, Wiisanen M, Aikat S, Kakavand B, Shah JS, Moliterno DJ, Gurley JC.
Inside-out access: a new method of lead placement for patients with central venous occlusions.
Heart Rhythm. 2011 Jun;8(6):851-7

[figure not shown]
This study described the experience of using the Inside-Out central venous access method to place pacemaker and defibrillator leads in 8 patients with upper body central venous occlusions that could not be crossed with conventional methods. IOCVA can be performed safely because there are consistent anatomic relationships adjacent to the thoracic central vein.

This study demonstrates that the inside-out central venous access can be successfully and safely applied to establish central venous access in patients with chronic, total SVC and subclavian vein occlusions that cannot be recanalized with currently available technology.

Eight patients were treated using off-the-shelf devices, physician modified for use in an IOCVA approach. All patients were referred for clinically indicated permanent pacemaker or defibrillator implantation in accordance with practice guidelines^{xxvi}. Additionally, all patients had chronic SVC, brachiocephalic, and/or subclavian vein occlusions that prevented a standard prepectoral transvenous approach to device implantation. The occlusions consisted of long segments of densely fibrotic lumen obliteration that could not be recanalized by conventional interventional techniques using a variety of guidewires, catheters, and dilators.

Occlusions were resistant to aggressive probing with 0.035-inch, stiff-shaft hydrophilic wires and supporting catheters. Probing was attempted from at least one direction and, in some cases, from both sides of the occlusion. None of the patients had collateral venous channels suitable for lead placement. An attempt at inside-out central venous access was offered after explanation of potential risks, including the possibility of risks not yet known for the procedure.

Figure 10: Images from pacing leads using IOCVA insertion methodology

All procedures were performed in a setting that was capable of managing major complications.

[figure not shown]
No clinical complications occurred except a for a small pocket hematoma that resolved without intervention.

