8.3.8 Safety Evaluations and Analyses

Adverse Events will be categorized by serious and non-serious, device or procedure-related and non-device or non-procedure related, and anticipated and unanticipated.

The frequency of each event will be summarized by seriousness, severity and by relationship to the device. Since some subjects may report the same event several times, the occurrence of the highest severity case of the event will be used for the purpose of analysis.

The rates of adverse events will be presented with associated 95% confidence intervals. No statistical hypothesis test will be made. At periodic intervals during study conduct, clinical evaluation of adverse events will be performed by the IDMC.

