9.1.2 Anticipated Adverse Events

A list of AEs which may be anticipated, resulting from use of the study device, are defined in Instructions for Use (IFU) of the investigational device and in Section 5.5 of this protocol.

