9.1.3 Serious Adverse Event/Unanticipated Adverse Device Effect

A Serious Adverse Event (SAE) is an AE that meets one of the following criteria:

- fatal
- life threatening
- results in an unanticipated or prolonged hospitalization
- results in a significant and persistent disability/incapacity
- results in a congenital anomaly or birth defect

An unanticipated adverse device effect (UADE) is any SAE as defined above that is caused by or associated with the device, if that effect, problem, or death was not previously identified in nature, severity, degree of incidence in this protocol.

Additionally, a UADE includes any other unanticipated serious problem associated with the device that relates to the rights, safety, or welfare of subjects.

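### The second primary safety endpoint counts only anticipated related events, although the stated safety objective has no such limit

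*Combined protocol and SAP*

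**What the plan says.** The synopsis, Section 6.4.2 and Section 8.2.1 give the second primary safety endpoint in the same terms: "Overall device and procedure related anticipated adverse events compared to historical safety data from CV placement procedures". Section 9.1.2 says that the anticipated events "are defined in Instructions for Use (IFU) of the investigational device and in Section 5.5 of this protocol". The Section 5.5 list is open-ended ("These potential risks include, but are not limited to") and gives no expected frequencies.

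The objective that this endpoint serves is worded more broadly. The synopsis bases safety on the "overall rate of acute complications using the study device as compared to historical rates of device/procedure related safety events using conventional CVA methods", with no restriction to anticipated events.

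Section 8.3.8 classes adverse events as "device or procedure-related and non-device or non-procedure related, and anticipated and unanticipated" and reports their rates with 95% confidence intervals and no test. Nothing in the protocol brings related but unanticipated events back into the second primary safety endpoint.

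The first primary safety endpoint is the absence of eight named complications: hemopericardium, hemothorax, pneumothorax, transfusion, resuscitation, emergency intervention after the procedure, ICU transfer and death. These count whether or not they were anticipated.

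**The concern.** The endpoint is narrower than its objective, and the part removed is the part that a premarket study of a new access route most needs to see. A related harm that nobody listed adds nothing to this rate.

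The restriction also falls on one side of the historical comparison. The Surfacer numerator is filtered by a Surfacer-specific list; the historical rates in Table 9 (Section 5.1) are not. A reader of the primary safety result could conclude that the device compares well with conventional access when some related events were never eligible to count.

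**Working it through.** **1. Which events count.** Setting Sections 5.5, 6.4.2, 8.3.8 and 9.1.2, Appendix A and Table 9 side by side gives:

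| Related event | Named in Section 5.5? | In second primary endpoint? |
|---|---|---|
| Nerve injury, lymphatic sequelae, vessel perforation, stroke | Yes | Yes |
| Harm new in nature, e.g. a mediastinal injury that fits no listed term | No | No, unless the IFU lists it |
| Catheter malposition | No | No, unless the IFU lists it |
| Failed catheterization | No | No, unless the IFU lists it |
| Minor hematoma | No | No, unless the IFU lists it |
| Listed serious harm reported as an unanticipated adverse device effect (UADE) for severity or incidence | Yes | Not stated |

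The IFU list is not part of the documents, so four rows are conditional on it. Minor hematoma does not come in under bleeding, because Appendix A requires a hemoglobin drop of at least 3.0 g/dL or transfusion of two or three units. Yet Table 9 and its footnote count malposition, local hematoma and failed catheterization on the historical side. Both complications behind the 2 of 136 in Table 4 (Section 4.1) were hematomas.

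**2. The plan's own precision figures.** With exact Clopper-Pearson limits, lower = Beta quantile(0.025; x, n − x + 1) and upper = Beta quantile(0.975; x + 1, n − x). For n = 30:
- x = 27 gives 73.5% to 97.9%
- x = 15 gives 31.3% to 68.7%

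Both agree with Section 8.2.2.

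**3. Size of the omission.** The planned n is 30, and the event counts below are assumptions. Each additional subject whose only related event is unanticipated is worth 1/30 = 3.3 points.

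| Subjects with an anticipated event | Further subjects with only an unanticipated event | Endpoint as written (95% CI) | All related events (95% CI) |
|---|---|---|---|
| 0 | 2 | 0/30 = 0% (0 to 11.6%) | 2/30 = 6.7% (0.8 to 22.1%) |
| 2 | 1 | 2/30 = 6.7% (0.8 to 22.1%) | 3/30 = 10.0% (2.1 to 26.5%) |
| 2 | 2 | 2/30 = 6.7% (0.8 to 22.1%) | 4/30 = 13.3% (3.8 to 30.7%) |
| 2 | 4 | 2/30 = 6.7% (0.8 to 22.1%) | 6/30 = 20.0% (7.7 to 38.6%) |

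A subject who already has a counted anticipated event adds nothing, so 3.3 points applies per subject, not per event.

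**4. Chance that it matters.** An unlisted related harm with true rate p occurs at least once in 30 subjects with probability 1 − (1 − p)^30. This is 26.0% for p = 1%, 45.5% for 2%, 59.9% for 3%, 78.5% for 5% and 95.8% for 10%. In each case its contribution to the endpoint as written is zero.

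**The case against.** The restriction has a rationale. The endpoint is a comparison with conventional access, and the historical data contain only recognised complication types; adding novel events to one side could make the comparison less like-for-like. That would carry weight if both sides used the same list, but Table 9 is not filtered by the Surfacer list. Keeping an anticipated-only line meets what remains of the argument.

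The Section 5.5 list is broad and open, so few events may fall outside it. That stands as a limit on size: the residue cannot be estimated. But an open list leaves the boundary to be judged after the event, which is a poor basis for a primary endpoint. Failed catheterization would also be expected to show in the efficacy results, but the historical comparison treats it as a safety event.

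A reader might infer more than the documents support, in five ways:

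- **That nerve, lymphatic or arterial injuries are missed.** Section 5.5 names nerve injury, lymphatic sequelae, vessel perforation, dissection and arteriovenous fistula. These count.
- **That a listed harm drops out once it proves worse or more frequent than expected.** Section 9.1.3 makes a device-associated serious event a UADE if it "was not previously identified in nature, severity, degree of incidence in this protocol". That is a definition for serious events; no text says that such an event stops being anticipated for the endpoint, and Section 5.5 states no incidence to exceed. The point is unsettled, not decided against the event.
- **That unexpected harms go unreported.** They stay in the Section 8.3.8 tables, and under Section 9.1.5 the results of a UADE evaluation go to the IDMC, FDA and investigators within 10 working days.
- **That primary safety as a whole is biased.** The first primary safety endpoint catches many severe harms whatever their mechanism.
- **That the protocol concedes unknown risks of this device.** The phrase "including the possibility of risks not yet known for the procedure" in Section 4.3 describes what was explained to patients in an earlier eight-patient series with physician-modified off-the-shelf devices.

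**Conclusion.** The point holds for the second primary safety endpoint only. As written, it leaves out related events outside the IFU and Section 5.5 lists, while the objective it serves has no such limit. Those events leave this primary rate but not the report.

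The direction is fixed, because the omission can only lower this rate. The size is 3.3 points per additional subject, assuming 30 subjects analysed; the number of such subjects cannot be known in advance. The intervals for 2/30 and 4/30 overlap heavily, so the illustration shows a shift in the headline rate and not a proven change of conclusion.

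It would also go too far to say that the restriction reverses a formal test. Against one Table 9 row, chosen by assumption (subclavian mechanical complications, 6.5% of 203, taken as 13/203), Fisher's exact p is 1.00 at 2/30, 0.25 at 4/30, 0.064 at 5/30 and 0.022 at 6/30. Crossing 0.05 from two anticipated cases therefore needs four unanticipated cases in other subjects, and the protocol fixes no comparator row. The change should be made, but the study's safety reporting does not fail without it.

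**What to change.** In the synopsis, Section 6.4.2 and Section 8.2.1, define the second primary safety endpoint as the proportion of subjects with at least one device- or procedure-related adverse event, anticipated or unanticipated, UADEs included. The same sentence settles the open question about listed serious harms reported as UADEs.

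Report the anticipated/unanticipated breakdown beneath it, and keep the anticipated-only rate as a supporting line for the historical comparison.

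The cost is wording in three places and one more table line. Section 8.3.8 already plans the classification by relationship and anticipation, so no new data are needed. The downside for the sponsor is a headline rate that may be slightly less favourable.
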